### **5.5.1 Pharmacokinetic Analyses**

Scatter plots of dose normalized plasma concentration and associated tabulations using n, mean, SD, percent coefficient of variation (% CV), geometric mean, median, minimum, and maximum will be generated by actual sample collection time and for each PK sample collection visit (Cycle 1 Day 1, Cycle 1 Day 15 and Cycle 2 Day 1). All PK data, which includes the complete bioanalytical results and time and date of blood draws and study drug administration recorded on the CRF, will be presented in subject listings. Plasma concentrations of lenvatinib and whole blood concentrations of everolimus versus time data will be analyzed using a population PK approach to estimate population PK parameters for each respective drug. For lenvatinib, data from this study will be pooled with historical data from other Phase 1 and 2 studies. For everolimus, data from this study will be pooled with data from Study E7080-G000-205. While pembrolizumab concentrations will be compared graphically to historical data. Analysis of serum antidrug antibodies (ADA) and neutralizing antibodies (NAb) to pembrolizumab will be described in a stand-alone report.

### **5.5.2 Pharmacodynamic, Pharmacogenomic, and Other Biomarker Analyses**

Soluble, tissue, genetic and/or imaging biomarkers (baseline and/or posttreatment) may be summarized using descriptive statistics. The correlation between biomarkers and clinical outcomes-related endpoints for safety and/or efficacy (including best overall response, PFS and OS) will be explored as appropriate. Details will be included in a separate analysis plan.

### **5.5.3 Pharmacokinetic-Pharmacodynamic Analyses**

The effect of lenvatinib in combination with everolimus or pembrolizumab on soluble, tissue, genetic and/or imaging biomarkers may be summarized using descriptive statistics in the PK/pharmacodynamic analysis set. PK/pharmacodynamic relationships (i.e., exposure-efficacy, and exposure-safety and exposure-biomarker relationships) may be explored for effects of study treatment. Efficacy endpoints will include the primary endpoint of PFS and other efficacy-related metrics including but not limited to ORR (based on RECIST 1.1) and OS. Safety endpoints will include most frequent AEs of special interest and dose reductions. Exploratory/graphical analyses will be conducted for PK/pharmacodynamic evaluations, and may be followed by model-based analyses. A detailed analysis plan will be provided separately later.

## 5.6 Safety Analyses

All safety analyses will be performed on the Safety Analysis Set. Safety data, presented by treatment groups will be summarized on an “as treated” basis using descriptive statistics (eg, n, mean, standard deviation, median, Q1, Q3, minimum, and maximum for continuous variables; n [%] for categorical variables). Safety variables include treatment-emergent adverse events (TEAEs), clinical laboratory parameters, vital signs, 12-lead ECG and echocardiogram results including left ventricular ejection fraction (LVEF). Study Day 1 for all safety analyses is defined as the earliest date of the first dose of study drugs.

### 5.6.1 Extent of Exposure

#### 5.6.1.1 Study Treatment Extent of Exposure

Duration of treatment for study medications individually and/or in combination (overall) will be summarized with descriptive statistics. The dosing end date will be imputed to the analysis cutoff date if the subject is still on treatment at the time of the data cutoff, and the dose will be imputed with the last dose recorded in the database for that subject.

The duration of individual study drug in months will be  $(\text{Date of the last dose} - \text{Date of the first dose} + 1) / 30.4375$ , including drug interruption days. For overall treatment duration, it is defined as the duration between the earliest first dose start date of study drugs and the latest last dose end date of study drugs.

#### 5.6.1.2 Study Drug Administration

Percentage of planned dose received, total dose, and dose intensity will be summarized with descriptive statistics. In addition, number of administrations will be presented for pembrolizumab.

The total dose per subject (mg) will be calculated as the sum of all doses per subject. The dose intensity (mg/day) for lenvatinib, everolimus and sunitinib will be calculated as:  $\text{Total dose (mg)} / \text{Duration of individual drug treatment (days)}$ .

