Dose modification guidelines for lenvatinib- (Arms A and B) and sunitinib- (Arm C) related adverse events should be followed for the management of hemorrhage. Either resume lenvatinib/sunitinib at a reduced dose or discontinue lenvatinib/sunitinib, depending on the severity and persistence of hemorrhage.

For subjects receiving treatment with sunitinib (Arm C) who experience hemorrhage associated with thrombocytopenia, treatment interruption is recommended; following resolution, treatment may be resumed at the discretion of the investigator.

Duration of Treatment

A subject will remain on study treatment until 1 or more of the following events occur(s):

- Progressive Disease (PD) (as confirmed by independent review)
Note: Subjects will be permitted to continue treatment beyond initial RECIST 1.1-defined progression as long as investigator-assessed clinical benefit is observed and the subject is tolerating study drug. Subjects will discontinue study treatment upon evidence of further progression and/or loss of clinical benefit as judged by the Investigator.
- Unacceptable toxicity
- Subject request
- Withdrawal of consent
- Completion of 35 treatments (approximately 2 years) with pembrolizumab
- Termination of the study by the Sponsor

The duration of treatment for each subject is estimated to be approximately 15 months.

Concomitant Drug/Therapy

Treatment (including blood products, blood transfusions, fluid transfusions, antibiotics, and antidiarrheal drugs, etc.) of complications of AEs or therapy to ameliorate symptoms may be administered at the discretion of the investigator, unless it is expected to interfere with the evaluation of (or to interact with) the study medication.

The following concomitant therapies are also **allowed**:

- Thyroid hormone suppressive therapy
- Adjuvant hormonal therapy for history of definitively treated breast or prostate cancer
- Anticoagulants including low molecular weight heparin (LMWH), warfarin, anti-Xa agents
- Antiinflammatory agents
- Bisphosphonates or denosumab
- Antihypertensive therapy (including additional antihypertensive treatment as appropriate if BP increases once the subject is enrolled)
- Palliative radiotherapy of up to 2 painful pre-existing, non-target bone metastases will be permitted without being considered PD

If the subject is receiving treatment with lenvatinib and requires surgery during the study, the stop time and restart time of lenvatinib should be as follows:

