## 3.2 Overall Study Design and Plan

[figure not shown]
This is a multicenter, randomized, open-label, Phase 3 study to compare the efficacy and safety of lenvatinib in combination with everolimus or pembrolizumab versus sunitinib as first-line treatment in subjects with advanced RCC.

Following the two stratification factors, i.e., geographic region (Region 1: Western Europe and North America or Region 2: rest of the world) and Memorial Sloan-Kettering Cancer Center (MSKCC) prognostic groups (favorable, intermediate and poor risk), Approximately 1050 eligible subjects will be randomized to one of the following three treatment arms in a 1:1:1 ratio, with approximately 350 subjects in each arm:

- Arm A: lenvatinib 18 mg (orally, once daily) plus everolimus 5 mg (orally, once daily)
- Arm B: lenvatinib 20 mg (orally, once daily) plus pembrolizumab 200 mg (intravenously [IV], every 3 weeks [Q3W])
- Arm C: sunitinib 50 mg (orally, once daily) on a schedule of 4 weeks on treatment followed by 2 weeks off (Schedule 4/2)

For the stratification factor of the geographic region, the Western Europe and North America region includes Austria, Belgium, Canada, France, Germany, Greece, Ireland, Italy, Netherlands, Poland, Spain, Switzerland, United Kingdom and the United States of America. The Rest of World region includes Australia, Czech Republic, Israel, Japan, Korea and Russian Federation.

This study is conducted in three study phases shown in Figure 1, a Pre-randomization Phase, a Randomization Phase, and an Extension Phase.

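### Sunitinib dose intensity in SAP 5.6.1.2 has no term for the 4/2 schedule, so a fully compliant subject scores anywhere from about 33.3 to 50.0 mg/day depending on the day treatment stops

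*SAP*

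**What the plan says.** SAP 5.6.1.2 builds dose intensity from two pieces. The numerator is plain: "The total dose per subject (mg) will be calculated as the sum of all doses per subject". The ratio is then set for three drugs together: "The dose intensity (mg/day) for lenvatinib, everolimus and sunitinib will be calculated as" that total divided by the duration of individual drug treatment in days. Pembrolizumab is left out of this formula.

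SAP 5.6.1.1 defines the duration as last dose date minus first dose date plus 1, "including drug interruption days". For subjects without an end date it adds two rules: "The dosing end date will be imputed to the analysis cutoff date if the subject is still on treatment", and "the dose will be imputed with the last dose recorded in the database for that subject".

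Neither section mentions scheduled rest. Lenvatinib and everolimus start as once-daily drugs without breaks. Sunitinib is given for 28 days and then stopped for 14 (SAP 3.2). SAP 5.6.1.2 also lists percentage of planned dose received, without a formula.

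**The concern.** A first-to-last-dose duration suits a drug taken every day. For a drug with built-in rest weeks it treats identical rests differently: those between courses are in the denominator, and the one after the last dose is not. Two subjects who both took everything prescribed can then have different dose intensities only because they stopped on different days of the six-week period.

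The trial is open-label with an active control. Readers will use Arm C exposure to judge how well the comparator was delivered. A figure that moves with stop day, and at full compliance always lies above the planned average, is a poor guide to that. The fill rule for ongoing subjects adds an ambiguity, because it does not say what is filled when the cutoff falls in a rest period.

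**Working it through.** The documents state no dose-intensity value, so there is no figure to reproduce. The check applies the SAP rule to a subject who takes 50 mg on days 1–28 of every 42-day period.

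**Inputs.** Dose and schedule: SAP 3.2. Numerator and ratio: SAP 5.6.1.2. Denominator and cutoff rules: SAP 5.6.1.1. Typical length: the protocol synopsis says "The duration of treatment for each subject is estimated to be approximately 15 months", which is 15 × 30.4375 = 456.6 days.

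**Planned average.** 50 × 28 / 42 = 33.3 mg/day.

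**Stopping at the end of the on-weeks of course k.** Total dose is 1400k mg and duration is 42k − 14 days, so dose intensity = 1400k / (42k − 14).

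**Stopping on the first day of course 2 (day 43).** (1400 + 50) / 43 = 33.7.

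| Day of last dose | Total dose (mg) | SAP dose intensity (mg/day) | Against 33.3 |
|---|---|---|---|
| 28 | 1,400 | 50.0 | +50% |
| 43 | 1,450 | 33.7 | +1% |
| 70 | 2,800 | 40.0 | +20% |
| 112 | 4,200 | 37.5 | +12.5% |
| 154 | 5,600 | 36.4 | +9% |
| 238 (about 8 months) | 8,400 | 35.3 | +6% |
| 448 (about 15 months) | 15,400 | 34.4 | +3% |

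Every row is full compliance. Over all possible stop days the value runs from 50.0 down towards 33.3 and never falls below it.

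**Effect on interpretation.** A subject on 50 mg in course 1 and 37.5 mg in course 2 who stops on day 70 scores (1400 + 1050) / 70 = 35.0. That is above the planned 33.3 and above a fully compliant subject at about 15 months (34.4), although only 2450 / 2800 = 87.5% of the planned dose was taken. A daily drug has no such effect: 20 mg taken on 70 of 70 days gives 20 mg/day.

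**Ongoing at cutoff, last rest day, two readings of the fill rule.**

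| Cutoff day | Rest filled at 50 mg | Rest filled at 0 mg |
|---|---|---|
| 42 | 2100 / 42 = 50.0 | 1400 / 42 = 33.3 |
| 84 | 3500 / 84 = 41.7 | 2800 / 84 = 33.3 |
| 462 | 16,100 / 462 = 34.8 | 15,400 / 462 = 33.3 |

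The first reading adds up to 14 × 50 = 700 mg; the second adds nothing.

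**The case against.** The strongest reply is that the plan does not rely on this number. It lists percentage of planned dose received, which could absorb the schedule. SAP 5.6.1.3 summarises sunitinib reductions and interruptions directly, with counts, reasons and time to first reduction, and 5.6.2.1 tabulates adverse events leading to them. Derivation detail is left to separate specifications. At the expected treatment length the discrepancy is about 3%, and mg/day is not comparable between different drugs anyway.

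Much of this stands. A reader might infer that the formula hides dose reductions in the control arm. The documents do not support that for the plan as a whole, because reductions are reported without using mg/day.

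Two parts do not stand. Percentage of planned dose received has no formula, and planned dose is not self-evident when treatment cycles last 21 days and the sunitinib schedule lasts 42. Even if well defined, it would not correct the mg/day figure reported beside it. And the dose-intensity formula is written out in the SAP, so a programmer who follows it gets the values above.

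**Conclusion.** The point holds as a minor defect in a descriptive summary. For sunitinib the stated rule gives a value that depends on stop day and is biased upward at full compliance: +50% at day 28, +20% at day 70 and about +3% at 15 months. No efficacy test or error rate is involved. The figures assume every dose is taken on schedule and the six-week calendar is not shifted.

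Two stronger readings should be avoided.

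- A reader might infer that dose intensity simply falls with time on treatment. It does not: day 43 gives 33.7 and the later day 70 gives 40.0. What matters is the position within the six-week period, with an effect that shrinks over time.
- A reader might infer that the cutoff rule certainly adds up to 700 mg for subjects in rest. SAP 5.6.1.1 refers only to the last recorded dose, and 5.6.1.3 treats 0 mg as a dosing state. If rest weeks are recorded as 0 mg, nothing is added. The text does not settle it, so the range is 0 to 700 mg.

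**What to change.** Make three linked changes to the SAP.

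1. In 5.6.1.2, for sunitinib, divide total dose by the scheduled on-days from first dose to last dose (or cutoff). Full compliance then gives 50 mg per on-day at every stop day: 1400 / 28, 1450 / 29, 2800 / 56 and 15,400 / 308 all equal 50. The subject reduced in course 2 scores 2450 / 56 = 43.75, which is 87.5%.
2. Define percentage of planned dose received for sunitinib with the same on-days. State how they are counted when dosing is interrupted. The protocol already counts cycles continuously regardless of interruptions, which suggests a fixed calendar from first dose.
3. In 5.6.1.1, state that for sunitinib subjects ongoing at cutoff the fill on scheduled rest days is 0 mg. This must accompany change 1: with on-days below the line, a 50 mg fill at day 42 would give 2100 / 28 = 75 mg per on-day.

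Do not extend the duration to the end of the last started 42-day period instead. A subject who took every dose and stopped on day 43 would score 1450 / 84 = 17.3 mg/day.

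The cost is SAP wording and a small change to the sunitinib exposure derivations. No new data are needed and treatment is unaffected.

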#### 5.6.1.3 Study Drug Dose Reductions and Interruptions

Reasons for dose reduction and interruption, time to the first dose reduction and time to the first dose interruption for lenvatinib, everolimus and sunitinib will be summarized. Dose reduction refers to the situation that a dose level was reduced from the previous dose level without going back.

In the combination of lenvatinib plus everolimus treatment arm, the starting dose of lenvatinib is 18 mg/day. Lenvatinib dose reductions occur in succession based on the previous dose level (14, 10, and 8 mg/day). The starting dose of everolimus is 5 mg every day. Everolimus dose may reduce to 5 mg every other day until everolimus discontinue. In the combination of lenvatinib plus pembrolizumab treatment arm, the starting dose of lenvatinib is 20 mg/day. Lenvatinib dose reductions occur in succession based on the previous dose level (14, 10, and 8 mg/day and so forth). The starting dose of pembrolizumab is 200 mg per administration. Pembrolizumab must be withheld/interrupted or discontinued for drug related toxicities and severe or life-threatening AEs. In sunitinib treatment arm, the starting dose of sunitinib is

50 mg/day on a Schedule 4/2 for subjects enrolled in Arm C. Sunitinib dose reductions occur in succession based on the previous dose level (37.5, 25 mg/day schedule 4/2).

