Dose reduction could be applied to lenvatinib (either 20mg/day or 18mg/day reduce to 14, 10, and 8 mg/day), everolimus (5 mg every day reduce to 5 mg every other day), and sunitinib (50 mg/day reduce to 37.5, 25 mg/day of schedule 4/2). Dose interruption could apply to all study drugs. Definition of dose interruption only includes the scenario that the before and after dose 0 (interruption period), the dose levels or dosing frequency are the same. For example: 20 mg lenvatinib followed by 0 mg and followed by 20 mg lenvatinib; 5 mg everolimus every day followed by 0 mg followed by 5 mg everolimus every day. If dose level reduces from previous dose level after dose interruption period (dose 0), it should count into dose reduction not dose interruption. For example: (1) 20 mg/day lenvatinib followed by 0 mg followed by 14 mg/day lenvatinib; (2) 5 mg everolimus every day followed by 0 mg followed by 5 mg everolimus every other day; the period with 0 mg should not count into dose interruption instead should count as dose reduction. If after dose 0 mg, the subject discontinued from treatment permanently, it should count as treatment discontinuation instead of dose interruption.

Number of subjects with dose reductions and dose interruptions of lenvatinib, everolimus, sunitinib, and pembrolizumab (dose reduction not applied to pembrolizumab) will be summarized by frequency counts and percentages according to study medication data.

Time to first dose reduction is defined as the date of the first dose to the date of first dose reduction, or the date of first dose interruption if subjects had dose interruption followed by dose reduction. There will be two ways to estimate the time to dose reduction. (1) Only include the subjects who had dose reduction events. Descriptive statistics will be generated to describe the time to first dose reduction for these patients. (2) Include all subjects. For subjects who did not have dose reduction, it will be censored at the date of last dose. For this summary, Kaplan-Meier method will be used to estimate the median time to first dose reduction for all the subjects by the treatment arms.

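### Sunitinib dose intensity on Schedule 4/2 moves with the day a subject stops, even at full adherence, and the cutoff imputation can credit drug to rest days

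*SAP*

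**What the plan says.** SAP 5.6.1.2 gives one rule for three drugs: "dose intensity (mg/day) for lenvatinib, everolimus and sunitinib will be calculated as" total dose over the duration of treatment with that drug, in days. SAP 5.6.1.1 defines the duration of an individual drug as last dose date minus first dose date plus 1, "including drug interruption days".

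For subjects still being treated, SAP 5.6.1.1 adds: "The dosing end date will be imputed to the analysis cutoff date if the subject is still on treatment" at the data cutoff, and "the dose will be imputed with the last dose recorded in the database for that subject".

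Sunitinib is the only one of the three drugs with planned weeks off. SAP 5.6.1.3 gives its starting dose as "50 mg/day on a Schedule 4/2 for subjects enrolled in Arm C", and SAP 3.2 spells the schedule out as 4 weeks on and 2 weeks off. SAP 5.6.1.1 and 5.6.1.2 make no allowance for it. Pembrolizumab, which also has planned gaps, is not named in the formula; for it the plan says "In addition, number of administrations will be presented for pembrolizumab".

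**The concern.** A mean daily dose over first-to-last-dose days is easy to read when dosing is meant to be continuous: a shortfall from the starting dose means doses missed or reduced. On a 4/2 schedule the same ratio also depends on where in the 42-day period the last dose falls. Each completed rest followed by another dose lowers the figure. The final rest never counts.

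The carry-forward rule adds a second inconsistency. A subject on treatment at cutoff may be in a scheduled rest. That rest now enters the denominator, and the numerator gains either nothing or 50 mg per day, depending on which dose was recorded last.

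At stake is whether the sunitinib row of the exposure table can be read as dose actually delivered. No hypothesis test, alpha level or efficacy estimate depends on it.

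**Working it through.** The documents state no sunitinib dose-intensity figure, so there is nothing to reproduce.

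**Inputs.** 50 mg on 28 of every 42 days (SAP 3.2 and 5.6.1.3). Duration = last − first + 1 (SAP 5.6.1.1), taken in days as SAP 5.6.1.2 requires. Expected treatment of about 15 months (Protocol Synopsis, Duration of Treatment), or 15 × 30.4375 ≈ 457 days.

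**Formula.** For full adherence with the last dose on day *j* (1 to 28) of course *k*, the last-dose day is d = 42(k − 1) + j, and

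DI = 50 × [28(k − 1) + j] / d.

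| Last-dose day | Position | Total dose / days | mg/day |
|---|---|---|---|
| 1 to 28 | course 1 | 50d / d | 50.0 |
| 43 | first day, course 2 | 1450 / 43 | 33.7 |
| 70 | last on-day, course 2 | 2800 / 70 | 40.0 |
| 85 | first day, course 3 | 2850 / 85 | 33.5 |
| 112 | last on-day, course 3 | 4200 / 112 | 37.5 |
| 196 | last on-day, course 5 | 7000 / 196 | 35.7 |
| 421 | first day, course 11 | 14050 / 421 | 33.4 |
| 448 | last on-day, course 11 | 15400 / 448 | 34.4 |

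The limit is 1400 / 42 = 33.3. Over all permitted last-dose days up to 457, the values are exactly 50.0 (stop by day 28) or 33.4 to 40.0, with nothing between 40.0 and 50.0. By stopping time, the range is 33.4 to 35.7 for 6 to 12 months and 33.4 to 34.5 for 12 to 15 months.

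**Overlap with real dose loss.** A subject who takes 20 of 28 doses, the first on day 1 and the last on day 28, scores 1000 / 28 = 35.7, the same as full adherence through course 5. A subject reduced to 37.5 mg for course 2 who stops on day 70 scores (1400 + 28 × 37.5) / 70 = 2450 / 70 = 35.0, above the never-reduced subject who stops on day 448 (34.4).

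**Cutoff imputation.** The first cutoff for a comparative analysis falls about 4 months after the last subject is randomized (SAP 6, Table 6), so subjects on treatment then have roughly 120 days or more. The earliest end-of-rest day after that is 126. With three adherent courses, the last dose on day 112, and imputed doses added to total dose:
- stopped on day 112: 4200 / 112 = 37.5
- on treatment, rest imputed as 0 mg: 4200 / 126 = 33.3
- on treatment, rest imputed as 50 mg: (4200 + 14 × 50) / 126 = 4900 / 126 = 38.9

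After 11 courses (day 462) the last two become 33.3 and (15400 + 700) / 462 = 34.8.

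**After the change.** Dividing by scheduled on-days gives 2800 / 56 = 50.0 at day 70 and 15400 / 308 = 50.0 at day 448. The reduced subject gets 2450 / 56 = 43.8 and the subject with missed doses 1000 / 28 = 35.7, so the three are now distinguished by dose alone.

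**The case against.** Total dose over elapsed days is a legitimate average, and a subject who stops on day 28 did receive 50 mg/day over those days. The overlap examples compare subjects with different durations; at the same stopping day the order is right (35.0 reduced against 40.0 adherent at day 70). The table reports group statistics, not ranks, and with about 15 months of expected treatment most of the spread has gone. Derivations are deferred to separate specifications (SAP 9), which might deal with the schedule. All of this limits the size. It does not remove the point: the SAP states the formula and names sunitinib, so a specification that corrected it would depart from the SAP.

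Three stronger readings are tempting, and the documents do not support them.

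- *Scheduled rests will be counted as interruptions.* SAP 5.6.1.3 says "Dose interruption could apply to all study drugs", and its definition has no explicit exception for planned rest. A reader might infer that every adherent sunitinib subject who starts a second course is counted. That requires rests to be stored as 0 mg records, which the documents do not show. The section also refers to dosing frequency, writes sunitinib dose levels as part of the 4/2 schedule, and summarises reasons for interruption, which a planned rest lacks. Protocol Table 5 treats interruption as a response to toxicity, separate from the 2 weeks off.
- *There is no adherence measure for sunitinib.* SAP 5.6.1.2 says "Percentage of planned dose received, total dose, and dose intensity will be summarized with descriptive statistics", with no restriction by drug. It gives no formula for any drug, which is missing detail and not a sunitinib error. A planned dose built on the 4/2 schedule would give 100% for an adherent subject at any stopping day.
- *The table is biased against Arm C.* The documents give no basis for a direction. The figure never falls below the schedule average of 33.3 at full adherence, so it looks low against 50 and high against 33.3.

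**Conclusion.** The point holds for the sunitinib denominator and for the cutoff imputation. At full adherence, stopping day alone moves the figure between 50.0 and about 33.4 mg/day. The wide part of that range is confined to early stoppers, and about 1 mg/day remains by 12 to 15 months. The imputation effect is up to 5.6 mg/day at day 126 (38.9 − 33.3) and 1.5 at day 462 (34.8 − 33.3).

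The denominator result rests only on rules stated in the SAP. The imputation result also assumes that imputed doses enter total dose and that the last recorded dose is 50 mg; with 0 mg recorded, no drug is credited to the rest. The consequence is limited to descriptive exposure tables. Efficacy results, discontinuation due to toxicity and time to treatment failure due to toxicity are unaffected. It is a minor point, worth making because it is so cheap to correct.

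**What to change.** In SAP 5.6.1.2, for sunitinib, define dose intensity as total dose divided by the number of scheduled on-days (28 per 42) between first and last dose. In SAP 5.6.1.1, impute sunitinib doses up to the cutoff on scheduled on-days only, and use the same on-day count in the denominator.

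Extending the duration through the final rest is not an adequate alternative. It gives 33.3 to subjects who stop at the end of an on-period, but a subject who stops on day 43 would score 1450 / 84 = 17.3.

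The cost is two sentences and the matching dataset specification before database lock, with no new data and no protocol change. There is one small downside: the sunitinib figure becomes mg per scheduled dosing day, and the table must say that it is not directly comparable with the mg per calendar day shown for lenvatinib and everolimus. The specification should also say how the 42-day grid is anchored after a prolonged interruption.

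Two clarifications are optional: state that scheduled non-dosing days are not dose interruptions, and give the planned-dose formula, which for sunitinib would be 50 mg × scheduled on-days.
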